7.5. Dose Selection

Based on the canine studies, 1 mg of rhIDU in a 20 kg dog with about 20cc of CSF (approximately 1 cc of CSF per kg body weight) resulted in 300 fold normal levels of enzyme in the meninges (the target tissue of this study), which are far above the levels necessary for effectively treatment. This dose is 0.05 mg/kg body weight, and 0.05 mg/cc CSF. Meningeal GAG reduction ranged from 57-70%, and pathologic studies showed that the majority of storage in cells is reduced or eliminated. This dose appears to be sufficient to achieve substantial reduction. At the lower 0.3 mg dose (0.015 mg/kg body weight or 0.015 mg/cc

CSF), substantial levels were also observed in the normal dogs in the brain suggesting that even at this dose meningeal levels would be far above required levels for treatment.

For an MPS I patient of 60 kg, there is about 120 cc of CSF. To obtain the same concentration as the 1 mg dose in dogs requires 6 mg of enzyme. Given the large fold excess (300 fold normal) achieved in the meninges at this dose, and since this is the first treatment in humans, a lower 1.74 mg dose (volume 3 cc) approximates the human dose comparable to the lower 0.3 mg dose studied in the dogs (0.029 mg/kg body weight, or 0.0145 mg/cc CSF). Higher doses could be considered in the future, if the data from this study suggest that higher doses are needed and safety is demonstrated at the lower dose.

By using 3 cc of enzyme with 6 cc of Elliotts B[®] solution in a 9 cc total injection volume, the enzyme is diluted 3 fold to reduce the impact of the high phosphate buffer and low pH of the drug formulation. The Elliotts B[®] solution is approved in the US and has been used routinely for the purpose of reducing the acidity of chemotherapy drugs during intrathecal administration.

7.6. Intrathecal enzyme replacement

The subject will be taken to a procedure room and placed on continuous pulse oximetry. Vital signs (pulse, respirations, blood pressure, pulse oximetry) will be recorded every 15 minutes. Temperature will be recorded before the procedure, then after the procedure on an every 4 hour schedule as described below.

Equipment and medications necessary for resuscitation will be in the room, along with qualified personnel. A peripheral intravenous catheter will be placed in a superficial vein, usually an arm, for administration of medication. The subject will receive 5 mg of midazolam (or as determined to be patient-appropriate for conscious sedation) with a normal saline flush. Depending on the hospital situation and local practice, general anesthesia may be preferred and is up to the discretion of the investigator with the consent of the subject, and approval of the local IRB or ethics committee.

A local anesthetic (lidocaine dose as appropriate) will be administered in the skin and underlying tissue above the chosen interspace. A small spinal needle will be inserted under sterile conditions into the lumbar spinal sac. A small amount of CSF (roughly 6-10 mL) will be collected for laboratory evaluations (refer to Section 7.7.4.1 below).

A dose of 3 ml of Aldurazyme (0.58mg/ml) or about 1.74 mg of recombinant α -L-iduronidase will be combined slowly and gently in a syringe with 6 cc Elliotts B[®] (or other equivalent solution as described below in Section 22.1) for a total volume of 9 mL. The syringe should be slowly inverted to mix, taking care to avoid creating small bubbles, shaking or shear in the solution. Dilution of the enzyme in Elliotts B[®] should be mixed immediately prior to injection. The Elliotts

B[®]-Aldurazyme[®] mixture should be administered as soon as possible and not later than 2 hours following mixing.

The diluted enzyme will be administered via lumbar puncture and given slowly over 2-3 minutes. The subject will be watched closely during enzyme administration for any adverse clinical reactions. After enzyme administration, the subject will lie supine in Trendelenberg (head below the level of the legs) for a period of one hour with monitoring continued. If the subject is unable to tolerate the Trendelenberg position, he or she may lie down in a position of comfort. The subject should be observed for another 3 hours supine or lying down in an alternative position of comfort. Subjects will remain hospitalized for a minimum of 24 hours from the time of the intrathecal injection. During hospitalization, vital signs, including pulse, respiration, blood pressure, pulse oximetry, and temperature will be checked every 4 hours. Neuro checks, including assessment of level of consciousness, sensation and movement, will be done q15 minutes during the first hour post-procedure, then hourly for the next 3 hours, and q4 hours thereafter during the 24 hour inpatient monitoring period. Discharge may not occur if any headache or pain greater than baseline for the subject are present. New narcotic analgesics may not be administered on an outpatient basis to study subjects. Family members will be provided clear instructions regarding the post discharge monitoring of the subject for anticipated adverse events. The day following discharge from the inpatient unit, the subject will return for an outpatient visit. A physical and neurologic examination and interim history will be performed. Re-hospitalization will occur if new neurologic symptoms, signs, or pain (greater than the subject's baseline) are present at this follow up visit. The above procedure will be followed for all subjects for all treatment visits.

Radiologically-guided lumbar puncture may be required in certain individuals due to body habitus or other factors. This will be performed under fluoroscopy or ultrasound guidance at the discretion of the investigator.

7.7. Other Study Procedures

7.7.1. Cognition

Neuropsychological testing will be performed at baseline and yearly using the following tests:

- CANTAB - the Cambridge Neuropsychological Test Assessment Battery (a sensitive and precise computerized non-language assessment battery that captures changes in cognitive performance on tests sensitive to frontal and temporal lobe functions [touch sensitive hardware and software required]),
- WASI - Wechsler Abbreviated Scale of Intelligence (4 subtest form - brief IQ measure),

- Hopkins Verbal Learning Test (measure of verbal declarative memory – multiple forms available for repeat testing), this is the primary outcome variable
- Brief Visual-spatial Learning Test (measure of visual declarative memory – multiple forms available for repeat testing), and
- TOVA (Test of Variables of Attention – computerized test of attention [hardware and software are needed])

7.7.2. Magnetic resonance imaging

MRI of the brain will be performed on a 3T MR scanner at baseline and yearly. MRI will be used to document changes in the following:

- Volumes: Whole brain, white matter, gray matter, hippocampal, caudate and ventricular volumes will be calculated using specialized software. Volumetric studies will use T1-weighted high-resolution structural MRI images, converted into 176 slices with a resolution of 1 mm isotropic voxels. As efforts to obtain a precise and reliable automated program have not been successful, manual measurement is needed for hippocampal structures, using the Image J v1.38 or later software. Reliability will be ensured within and across raters.
- White matter changes and Virchow-Robin spaces: assessed using the methodology in Matheus et al. 2004. See Appendix C.
- Diffusion Tensor Imaging and Tractography to examine white matter structure and function will use 12 directional diffusion weighted imaging to calculate fractional anisotropy (FA) with the corpus callosum measure on the midsagittal section as the Region of Interest (ROI). We will also examine connectivity of the afferent and efferent pathways from the hippocampus to the rest of the brain using the fornix as the ROI if possible.

If a subject has a programmable ventriculoperitoneal shunt, it may need to be reprogrammed after the MRI. This should be supervised by a neurosurgeon or physician trained to analyze and reset the programmable shunt. The analysis and reprogramming of the shunt may require up to three plain x-rays of the shunt.

The neuropsychological tests and brain MRI may be done as part of a separate study being conducted at the University of Minnesota. If these tests have been performed within 60 days of enrollment in MIRC-002, then this data may be used as baseline data for this extension study.

7.7.3. Clinical evaluations

Clinical evaluations as described below will be completed at the study site and documented on Case Report Forms.

7.7.3.1. History and Physical Examination

A history and physical examination will be performed at each visit. A detailed and thorough medical history will be obtained at screening. Specific information relating to any prior or existing medical conditions/surgical procedures involving the following systems: Infectious Diseases, Allergy, Metabolic/Endocrine/Nutritional, Hematopoietic, Musculoskeletal, Dermatologic, HEENT (Head, Ears, Eyes, Nose, and Throat), Breasts, Respiratory (including supplemental O₂, presence/absence of tracheostomy, mechanical ventilation requirement), Cardiovascular, Gastrointestinal/Hepatic, Genitourinary/Renal, Neurologic (ambulatory status), and Psychiatric/Psychosocial. An interim history will be obtained at each subsequent visit.

Each physical examination will include the following physical observations: General Appearance, Skin, HEENT, Lymph Nodes, Heart, Chest, Abdomen (including degree of Hepatosplenomegaly), Extremities/Joints. A Snellen test will be performed at each visit by a standard, age or intellect-appropriate eye chart 20 feet from the subject in a well-lighted, indoor space, with each eye examined individually while the opposite eye is covered.

If clinically significant worsening from the baseline medical status or vital signs status is noted, the change will be documented as an AE on the appropriate data collection sheet and will be followed as an adverse event consistent with the procedure outlined in Section 11.3. Clinical significance is defined as any variation in physical findings, which has medical relevance resulting in an alteration in medical care.

7.7.3.2. Neurologic examination

A neurologic examination including mental status, cranial nerves, motor, sensory, associated motor, and reflexes will be conducted at each visit. Mental status exam will include assessment of level of consciousness and the Mini-Mental State Examination (MMSE). Although more commonly used as a screening exam in adults, the MMSE has been studied in children as young as age four, and has been shown to correlate with chronologic and mental age (Ouvrier et al., 1993). We will use the minor modifications to the MMSE as detailed in the Ouvrier paper (Appendix A).

7.7.3.3. Photography and Video

Photographs and/or video of the subjects may be taken at baseline and each visit to record the subject's appearance, posture, gait, physical and neurologic findings, and document any changes occurring in the subjects with time. Photography and video is optional at the discretion of the investigator and willing participation of the subject.

7.7.3.4. Six minute walk test

The subject will be given a six-minute walk test according to American Thoracic Society guidelines (ATS statement, 2002), except that the course distance will be 15 meters.

7.7.3.5. Subjective response of clinical symptoms

The subject will be asked at baseline to verify if they have the following symptoms: headache, memory loss, difficulty concentrating, decreased ability to function at work or school or in their daily life. Also, the subject may identify additional CNS symptoms that concern them. At each subsequent visit, the symptoms should be scored by the subject as no change (score 0), slightly better (+1), moderately better (+2), much better (+3), slightly worse (-1), moderately worse (-2) or much worse (-3).

7.7.3.6. Independence of functioning scale

A modified Functional Independence Measure (FIM) score will be determined (Maynard et al., 1997). The modified FIM will evaluate the following areas of functioning: self-care, sphincter control, mobility, and locomotion. The subject will be asked to assign a score to each item in these areas. A parent or guardian may assist the subject in completion of the FIM score. Further description of the FIM score is detailed in Appendix B.

7.7.4. Laboratory tests

The following laboratory tests will be performed as described with test reports forwarded to the designated study staff.

7.7.4.1. CSF analyses

7.7.4.1.1. CSF chemistry and cell counts

Approximately 6-10 mL of CSF, roughly equivalent to the injection volume, will be withdrawn from each subject at each lumbar puncture for all CSF evaluations. A portion of this sample (~ 1 cc) will be used for determination of glucose, protein, and cell counts. Specimens will be collected and processed at each study site in a laboratory conforming to the local standards and regulations. The subject's levels will be compared to age-matched normative controls from that laboratory.

7.7.4.1.2. CSF GAG content

A portion of the CSF (~1cc) will be frozen and shipped on dry ice to a specialty laboratory for subsequent glycosaminoglycan analysis. Sulfated glycosaminoglycans will be assayed using a modification of the dimethylene blue dye method as published (Whitley et al., 1989). The GAG quantities will be determined by comparison to standards of dermatan sulfate.

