6.4. Study Timelines

The duration of each subject's participation in the study is expected to be five years. We anticipate enrolling these subjects over a 4-year period. The estimated date of completion of the study is 10 years following the onset of the study.

7. Procedures Involved in the Human Research

This study is a five-year open-label, prospective trial in 6 MPS I subjects age six years or greater who have completed a 24-month open label study (MIRC-002). Potentially eligible subjects who (or, if appropriate whose parents or guardians) have provided signed, written informed consent will first participate in a baseline screening phase. This will occur at least six months after subjects have completed the MIRC002 pilot study. During baseline screening, the subjects will receive the baseline evaluations outlined below, and their eligibility will be determined. Every three months, subjects will receive intrathecal recombinant human α-L-iduronidase (IT rhIDU) approved as Aldurazyme® [laronidase] for the treatment of cognitive impairment in patients with mucopolysaccharidosis I (MPS I). Neuropsychological testing and MRI will be performed at baseline and at one year intervals. Safety will be monitored continuously throughout the subject's study participation through recording all adverse events (AEs) and periodically performing clinical and laboratory evaluations.

Study subjects will receive intrathecal enzyme therapy only during the study; intrathecal enzyme therapy will not be administered at the end of the five-year period. If further intrathecal enzyme is desired, the subject may enroll in further intrathecal research if another study is available.

To assure that subjects enrolling in the trial have maximum access to alternative therapy, subjects will be asked to receive counseling regarding other available appropriate medical and surgical alternatives prior to enrollment in this trial.

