7.8.2.4. Laboratory tests

CSF GAG content

At the each lumbar puncture, a portion of CSF will be quick frozen for subsequent glycosaminoglycan analysis. Sulfated glycosaminoglycans will be assayed using a modification of the Alcian Blue method of Bjornsson as published (Whitley et al., 1989). The GAG quantities will be determined by comparison to standards of dermatan sulfate.

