9.3.3.1. Laboratory evaluations: CSF and anti-IDU antibody

Absolute, percent, and reference range change in CSF glucose, protein, and cell counts from the month 0 visit to the subsequent month visits will be calculated for each subject, and summarized over subjects with means, standard deviations, and 95% confidence intervals. Frequency and percent of subjects with values outside their reference range will be reported.

Absolute and percent change ELISA anti-IDU antibody from the month 0 visit to the subsequent month visits will be calculated for each subject, and summarized over subjects with means, standard deviations, and 95% confidence intervals. Frequency and percent of subjects with values outside their reference range for the subject's age will be calculated.

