9.3.3.4. Other Adverse Events

Other adverse events and unexpected adverse events from the time of injection to the time of subsequent injection will be recorded for each subject. The frequency and percent of subjects experiencing any such event will be tabulated for each post-injection interval, and for the entire month 0 to end study interval.

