9.3.4.2.4. Biochemical

Absolute and percent change from the month 0 visit to the final study visit in glycosaminoglycans (GAG), will be calculated for each subject, and summarized by presenting means, standard deviations, and 95% confidence intervals.

10. Confidentiality

Local transport of the Case Report Forms, source documents and specimens will be limited to the site's authorized staff. Study participants and/or respective guardians will be informed that information that identifies them or their child will be used only for the purpose of the study; this includes information that can help study personnel locate or contact them as well as information related to their or their child's medical condition (medical records, for example).

Data and specimens will be stored locally for at least 11 years as previously described. While the study is active, access to the stored data and specimens will be limited to approved study staff. After the study is closed, local access will be limited to the site's PI(s).

11. Certificate of Confidentiality

To help protect participant privacy, a Letter of Confidentiality has been obtained from the National Institutes of Health (NIH). With this Certificate, the researchers cannot be forced to disclose information that may identify a study participant, even by a court subpoena, in any federal, state, or local civil, criminal, administrative, legislative, or other proceedings. The researchers will use the Certificate to resist any demands for information that would identify a participant, except as explained below.

The Certificate cannot be used to resist a demand for information from personnel of the United States Government that is used for auditing or evaluation of Federally funded projects or for information that must be disclosed in order to meet the requirements of the federal Food and Drug Administration (FDA).

Even with the Certificate of Confidentiality, the investigators continue to have ethical obligations to report child abuse or neglect and to prevent an individual from carrying out any threats to do serious harm to themselves or others. If keeping information private would immediately put the study participant or someone else in danger, the investigators would release information to protect the participant or another person.

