14.1. Subject withdrawal

A subject (or the legal guardian acting on behalf of the subject) is free to withdraw consent and discontinue participation in the study at any time, and without prejudice to further treatment, according to standard clinical practice. A subject who decides to discontinue participation in the study should be contacted to obtain information about the reason(s) for discontinuation and collection of any potential AEs.

All data acquired prior to termination for the reasons outlined below will be included in the primary analysis unless a participant withdraws consent. A subject's participation in the study may be discontinued at any time at the discretion of the investigator. The following may be justifiable reasons for the investigator to remove a subject from the study:

- The subject is uncooperative or non-compliant with the protocol.
- The subject develops an exclusion criterion or concurrent disease.
- The subject develops a condition or adverse event that, in the opinion of the investigator, contraindicates the continuation of treatment.
- The subject desires a surgical procedure or other alternative treatment for cognitive decline.

The reason for withdrawal should be clearly described. Withdrawn subjects may not re-enter the study. Follow-up procedures will be required if the subject discontinues as a result of an adverse event. Follow-up may include completing the study assessments scheduled at the final visit. Every effort will be made to conduct a final study visit with the participant, and participants will be followed clinically until, if applicable, all adverse events resolve.

If a subject or the subject's legal guardian, acting on behalf of the subject, discontinues participation in the study, or the subject is discontinued by the

investigator, the Patient Completion/Discontinuation Case Report Form (CRF) describing the reason for discontinuation must be completed. Any AEs experienced up to the point of discontinuation must be documented on the AE CRF. If AEs are present when the subject withdraws from the study, the subject will be re-evaluated within two weeks of withdrawal. If AEs are not resolved, additional follow-up will be performed, as appropriate.

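### Do two assay names and a blank End Study cell leave the CSF GAG change undefined?

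*Combined protocol and SAP*

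**What the plan says.** **Assay.** Section 7.7.4.1.2 states that sulfated GAG in CSF are "assayed using a modification of the dimethylene blue dye method as published". Section 7.8.2.4 states that they are "assayed using a modification of the Alcian Blue method of" a cited author. Both sections cite the same 1989 publication and calibrate against dermatan sulfate.

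**Analysis.** Section 9.3.4.2.4 reads: "Absolute and percent change from the month 0 visit to the final study visit in glycosaminoglycans (GAG), will be calculated for each subject". The summary is a mean, SD and 95% confidence interval, with no test.

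**Sampling.** Table 1 (section 7.2) marks CSF GAG in the odd- and even-numbered visit columns, the two in which intrathecal rhIDU is given. Baseline and End Study are blank. Section 7 adds that "intrathecal enzyme therapy will not be administered at the end of the five-year period", so no treatment puncture is planned then. Section 7.8.2.4 ties collection to the puncture: "At the each lumbar puncture, a portion of CSF will be quick frozen".

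**Visit terms.** Month 0 is not a Table 1 column. It serves as the reference for CSF safety tests in section 9.3.3.1 ("Absolute, percent, and reference range change in CSF glucose, protein, and cell counts from the month 0 visit to the subsequent month visits") and for adverse events in section 9.3.3.4 ("and for the entire month 0 to end study interval"). Section 14.1, on withdrawal, says: "Every effort will be made to conduct a final study visit with the participant".

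**Matrix.** The section 1 objective is GAG storage in CSF. The list of stored data in section 8 instead has a serum GAG entry, which no procedure produces.

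**The concern.** GAG is the only variable in the planned biochemical analysis. If two assays were used, or the method changed during five years, a within-subject change could mix a treatment effect with a method difference. If the final study visit means the End Study column, no GAG value is scheduled there and the planned change has no end point. If month 0 means Baseline, the starting value is missing too. With no more than six subjects, the choice of first and last sample directly sets the reported mean and interval, so an analyst should not be left to make it after seeing the data. The serum entry in section 8 adds doubt about which fluid is meant.

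**Working it through.** The plan gives no figure to reproduce. The check compares sections and then counts visits.

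**1. What the end-point wording must mean.** Four outcomes, with their cells in Table 1:

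| Measure (section) | End point in the text | Baseline | Treatment visits | End Study |
|---|---|---|---|---|
| Hopkins test (1) | subject's final visit | marked | yearly | blank |
| Brain MRI (9.3.4.2.2) | final study visit | marked | yearly | blank |
| Walk test, FIM (9.3.4.2.3) | final study visit | marked | marked | marked |
| CSF GAG (9.3.4.2.4) | final study visit | blank | marked | blank |

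If the end point had to be the End Study column, the MRI change, and the primary Hopkins change as section 1 words it, would be missing as well. If it means the last visit at which the measure is scheduled, all four rows work. For the walk test and FIM that visit is End Study itself.

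**2. Month 0.** For MRI it has to be Baseline, since the first scan is marked there. For CSF measures it has to be Visit One, the first marked sample. Section 9.3.3.1 uses month 0 for CSF glucose, protein and cell counts, which Table 1 marks at the same visits as GAG. Section 7.6 collects CSF before the enzyme is injected, so the Visit One sample precedes the first dose of this study. Baseline and Visit One lie five days to three months apart.

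**3. How much follow-up the last sample gives up.** Inputs are three-month spacing from Visit One (Table 1 note), five years of participation (section 6.4) and no dose at the end (section 7).

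- Five years counted from Visit One: treatment visits at months 0, 3, ..., 57, which is 57/3 + 1 = 20 visits. The last sample is at month 57, and 60 − 57 = 3 months before the end. It covers 57/60 = 95% of the period.
- Five years counted from Baseline, with the longest gap of 3 months: the end falls 57 months after Visit One. Treatment visits run at months 0, 3, ..., 54, which is 54/3 + 1 = 19 visits, and the last sample again comes 3 months before the end.

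A first and a last CSF GAG value are scheduled for every subject with at least two treatment visits. A subject with one such visit contributes no change.

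**4. Does the assay name alter the result?** Section 7.7.4.1.2 sends the samples to a specialty laboratory. No section says that both methods are run or that one replaces the other. Suppose, as an assumption, that the two methods differ by a constant factor *k*. With one method throughout, percent change is (*k*·last − *k*·first)/(*k*·first) = (last − first)/first, so *k* cancels. Absolute change is multiplied by *k* and is read in the units of the method reported. A spurious change would need a switch of method between a subject's two samples. The documents give no sign of a switch and no between-method difference.

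**5. Matrix.** Section 1, the CSF block of Table 1 and the headings of the CSF GAG text in sections 7.7.4.1.2 and 7.8.2.4 all say CSF. The section 8 list is not complete: it also omits CANTAB, WASI and CSF iduronidase. The serum entry is a slip.

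**The case for a change.** The strongest case for acting is that month 0 and the final visit carry different meanings for different measures, that section 14.1 uses the closing visit in a sense close to End Study, and that a few words would settle the matter. With six subjects at most, such choices are better written down beforehand. A broad reading of collection at each lumbar puncture would also take in the baseline flow-study puncture (section 7.7.5.1), giving a second candidate for the first value.

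The drafting criticism stands: the terms are undefined and the assay names differ. The consequence does not. Section 14.1 deals with withdrawal and does not define the analysis term. Table 1 marks no CSF test at the flow study, and section 7.7.4.1.1 relates the volume withdrawn to the injection volume, which points to treatment punctures. That leaves one scheduled first sample and one scheduled last sample per subject, so there is little room for selection.

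Follow-up to the last sample will differ between subjects who complete and subjects who withdraw. That is true of any change to a last visit, and section 9.3.2 already summarizes enrollment duration and the number of intrathecal doses.

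**Conclusion.** The inconsistencies are real but clerical, and no change to the plan is needed. The two assay names share one citation and one standard and most likely describe a single laboratory method. The Study Operations Manual, which Table 1's introduction cites for test guidelines and central-laboratory samples, may settle the name; it is not among the documents. The GAG change can be computed from samples already scheduled, from Visit One before dosing to the last treatment visit, at a cost of about 3 months out of 60. The fluid is CSF. The outcome is secondary and descriptive, no decision rests on it, and no bias or lost data is shown.

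This rests on two assumptions: one method is used for all of a subject's samples, and analysts take the first and last scheduled CSF values. Evidence that the laboratory changed method partway through a subject's follow-up would reopen the point.
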